## Exec Summary

Dry eyes is an extremely common symptom that affects as many as 337 million people globally. Almost everyone has probably had or will have dry eyes at some point in their life. Common treatment to dry eyes is by using lens lubricant or eye drops which gives short relief and comfort. Sufferers would have to endure the discomfort of having to instill drops frequently for which will indirectly affect their work and quality of life. This study will determine the role of VCO therapeutic contact Lens in changing the tear volume and improving tear stability on dry eyes patients by giving a long relief and effective remedy.

The study will be conducted at UKM Optometry Clinic using randomized, double-masked on 50 dry eye subjects in 4 different phases. Measurement of tears before and after (15 minutes) the therapeutic VCO contact lens are worn by the subjects will be recorded. Similar parameter will be measured 15 minutes post wear (Phase 1 & 2). The intra-variability and inter-variability of the parameters will also be measured accordingly after 2 months (Phase 3 & 4).

The outcome of this study is expected to enhance the volume and stability of tears in dry eye subjects. Sufferers of these symptoms will find prolonged relief through this new knowledge of management, thus will improve the quality of life of people who has dry eyes problems.

VCO therapeutic contact lens may provide the solution of prolonged relief for dry eye symptoms. This will provide a new knowledge amongst eyecare practitioners in managing patients with dry eyes due to ocular disease or environmental factors and using a local product will indirectly boost the economic growth of Malaysia.

## Problem statement

It is known that VCO drops used as ocular rewetting agent on rabbit eyes has been tested and proven safe and effective in increasing tear volume. It has also been tested on humans with success. However, the use of contact lens as a vehicle to transfer the VCO need to be further investigated. It is significantly important to know the role of VCO therapeutic contact lens in changing the tear volume and stability in dry eye patients. Hence, this study will determine if VCO Therapeutic Contact Lens changes the tear volume and stability in dry eye patients.

## Hypothesis

VCO Therapeutic Contact Lens can be significantly used to improve tear volume and tear stability in dry eye subjects.

## Objective

The main aim of research is to investigate the changes of tear volume and tear stability from VCO Therapeutic Contact Lens wear.

The following specific objectives are: -

- (i) To determine the tear break up time (TBUT) and tear volume (Schirmer's Test) at 0 and 15 minutes after therapeutic VCO contact lens wear.
- (ii) To determine the tear break up time (TBUT) and tear volume (Schirmer's Test) at 15 minutes after lens removal.
- (iii) To measure the inter-variability and intra-variability of the parameters measured for TBUT, after therapeutic VCO contact lens wear

## Research Question

## Literature review

Dry eye is an ocular condition which is characterized by reduction in tear volume, tear stability and increase in tear osmolarity as well as water evaporation. Visual disturbances including blurriness, visual discomfort and damage of the ocular surface are the most common dry eye-related sign and symptoms. Previous study had reported that 25 % of patients who visited ophthalmic clinic may report symptoms of dry eye. Thus, making this condition as one of the public health. The current study of dry eye prevalence of in Kuala Lumpur, Malaysia, showed the results of estimation that around 15% of the sample population suffering dry eye (Kaur et.al., 2016). However, the prevalence of dry eye varies between countries and was estimated to be around 7.4% to 33.7% (Buckley, 2018).

To ensure the accuracy of dry eye diagnosis, different tests of tear parameters including tear quantity and quality tests are used to detect the pre-existing condition (Masmali et al. 2016). One of the ways to assess for tear quality is by assessing the stability of the tear film which can be obtained through tear break up time (TBUT) measurement. Tear quantity can be obtained by measuring the tear volume and Schirmer's test is one of the objective measurements that is widely used by the practitioner to measure it (Miyake et. al, 2016). It becomes practically important as stability of the tear film and sufficient composition of each substances such as lipid, mucin, electrolytes, and including aqueous humor, are crucial in order to know the integrity of the tear film layer (Buckley, 2018).

At present, there are few dry eye remedies available in the market. Among all of those remedies, artificial tear and eye lubricants are still the most common initial management and prophylaxis that will be given by medical practitioners to dry eye patient regardless of the type of dry eye. Artificial tear is well known to given temporary relief of dry eye's sign and symptoms. Though, it might not be an effective treatment as they only contain polymers that is able to lubricate ocular surface and lack of numerous important biological factors such as antimicrobial growth and anti-inflammatory factors that present in natural tear and important to maintain ocular surface homeostasis (Mutalib et al. 2015)

Virgin coconut oil (VCO) is known as a local functional food and contain antiviral and anti-microbial agents (Marina & Man 2016). Study has been conducted on efficacy of VCO as ocular rewetting agent on rabbit eyes. It has been shown that VCO did not cause harmful effects when used on rabbit's eyes. The fatty acid and anti-inflammatory agents on VCO may act as protective layer over the tear film layers to reduce evaporation, which is useful for those with dry eyes problem (Mutalib et al. 2015). Similar study was done on human and it was found to increase the tear volume (Macmonnies, 2018)

However, one of the discomforts when using the VCO, it is oily and messy when used directly on eyes and it also causes temporary blurriness. In another successful study, contact lenses were used as a medium or vehicle of transportation of VCO to human eyes (Hussin, 2014). The contact lenses were immersed in a volume of VCO for several hours before placing it on the human eyes. In this study, VCO extracts will be injected out and will be vehicle to the eye by using hydrogel contact lens. This study will investigate the role of VCO Therapeutic Contact Lens in changing the tear volume and tear stability in dry eye subjects.

## STATISTICAL ANALYSIS

After the data has been collected, IBM SPSS Statistics Version 25 (Armonk, NY, USA) will be use to analyze the data. The assessment of the efficacy will be based on the all subjects who completed the study. Shapiro-Wilk test will be used to test the normality of the data as the sample size is less than 100. All results are expressed as Mean  $\pm$  SD. **Parametric test of Repeated Measured Anova** will be used to analyze the statistical difference of before, immediately and after treatment if the data is normally distributed. A probability value ( $p$ -value)  $<0.05$  will indicate that the data is statistically significance.

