#### **Phase 1**

First measurement of TBUT (Mcmonnies, 2018) on both eyes will be taken before lens insertion. Then, subjects will be fitted with therapeutic VCO contact lens on one of their eyes and a placebo hydrogel contact lens on the other eye which acts as a control. The contact lenses will be fitted in randomized manner by a mask operator. Subjects will wear the contact lenses for 15 minutes. After the 15th minute, both contact lenses will be removed and second measurements of TBUT will be done. All tear breakup time (TBUT) measurements will be taken three times and the average value will be used as the data. These will be the immediate measurement after therapeutic VCO contact lens wear. Subjects will be given 15 minutes time interval before a re-measurement of TBUT test again. Once all the measurements are taken, subjects will be discharged from the study before being called again in Phase 2. From the data collected, an analysis will assist to understand the mechanism of tear integrity when VCO therapeutic contact lens is used on dry eyes.

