#### **Phase 2**

First measurement using Schimer's Test (Miyake et al, 2016) on both eyes will be taken before lens insertion. Then, subjects will be fitted with therapeutic VCO contact lens on one of their eyes and a placebo hydrogel contact lens on the other eye which acts as a control. The contact lenses will be fitted in randomized manner by a mask operator. Subjects will wear the contact lenses for 15 minutes. After the 15th minute, both contact lenses will be removed and second measurements of Schimer's Test will be done. All measurements will be taken three times and the average value will be used as the data. These will be the immediate measurement after therapeutic VCO contact lens wear. Subjects will be given 15 minutes time interval before a re-measurement of Schimer's Test again. Once all the measurements are taken, subjects will be discharged from the study before being called again in Phase 3. From the data collected, an analysis will assist to understand the mechanism of tear volume changes when VCO therapeutic contact lens is used on dry eyes.

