#### **Phase 3**

In Phase 3 a repeat will be done to measure the TBUT (2 months after the first fitting) where lenses will be refitted at random to check on inter-variability. First measurement using TBUT Test on both eyes will be taken before lens insertion. Then, subjects will be fitted with therapeutic VCO contact lens on one of their eyes and a placebo hydrogel contact lens on the other eye which acts as a control. The contact lenses will be fitted in randomized manner by a mask operator. Subjects will wear the contact lenses for 15 minutes. After the 15th minute, both contact lenses will be removed and second measurements of TBUT Test will be done. All measurements will be taken three times and the average value will be used as the data. These will be the immediate measurement after therapeutic VCO contact lens wear. Subjects will be given 15 minutes time interval before a re-measurement of TBUT Test. Once all the measurements are taken, subjects will be discharged from the study before being called again in Phase 4. From the data collected, an analysis will assist to understand the inter-variability between the measurement done in Phase 1 and Phase 3.

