#### **Phase 4**

In Phase 4 a repeat will be done to measure the TBUT (2 months after Phase 3) where lenses will be refitted at random to check on intra-variability. First measurement using TBUT Test on both eyes will be taken before lens insertion. Then, subjects will be fitted with therapeutic VCO contact lens on one of their eyes and a placebo hydrogel contact lens on the other eye which acts as a control. The contact lenses will be fitted in randomized manner by a mask operator. Subjects will wear the contact lenses for 15 minutes. After the 15th minute, both contact lenses will be removed and second measurements of TBUT Test will be done. All measurements will be taken three times and the average value will be used as the data. These will be the immediate measurement after therapeutic VCO contact lens wear. Subjects will be given 15 minutes time interval before a re-measurement of TBUT Test. Once all the measurements are taken, subjects will be discharged from the study before being called again in Phase 4. From the data collected, an analysis will assist to understand the inter-variability between the measurement done in Phase 1 and Phase 3.

This study is at low risk as the subjects will not have any 'drop-out' issues and is anticipated to be able to go through the clinical trial successfully as the procedure only takes less than half an hour and in case of emergency, a medical officer is being put on standby.

The VCO therapeutic contact lens after used will also be tested for biocompatibility test as per ISO 10993 for Ocular Irritation Test (ISO 10993-10:2010 (E), Acute systemic toxicity test (ISO 10993-10:2010 (E), Skin Sensitization Test (ISO 10993-10:2010 (E), In Vitro Cytotoxicity : Direct Contact Method (ISO 10993-5:2009 (E) by accredited laboratory. This will be monitored by a toxicologist (co-researcher) and manufacturing is done by Supervision Optimax Sdn Bhd (industry collaborator).

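### Basing efficacy on subjects who completed the study can discard finished Phase 1 and Phase 2 data from anyone who misses a later repeat visit

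*Combined protocol and SAP*

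**What the plan says.** The analysis set is fixed by one sentence under STATISTICAL ANALYSIS: "The assessment of the efficacy will be based on the all subjects who completed the study". The section does not define completion and gives no other analysis set or missing-data rule. The test it names, a repeated-measures ANOVA, compares the readings before, immediately after and later after wear.

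The Exec Summary describes a study "on 50 dry eye subjects in 4 different phases". Phase 1 measures TBUT and Phase 2 measures Schirmer, each with all three readings at a single visit. Phase 3 repeats TBUT 2 months after the first fitting: "lenses will be refitted at random to check on inter-variability". Phase 4 repeats it again: "2 months after Phase 3) where lenses will be refitted at random to check on intra-variability". Under Objective, items (i) and (ii) are the TBUT and Schirmer changes, and item (iii) is the variability of TBUT.

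Phase 1 closes with "Once all the measurements are taken, subjects will be discharged from the study before being called again in Phase 2", and Phases 2 and 3 close in the same way for the phase that follows. The last paragraphs under Phase 4 expect no drop-outs because the procedure takes less than half an hour.

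**The concern.** Membership of the efficacy set appears to depend on visits that the efficacy endpoints do not need. Someone who attends Phases 1 and 2 and then does not return has contributed everything required for objectives (i) and (ii). On the natural reading, that subject is still removed from both analyses.

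Two things are at stake. The first is precision, which is lost whatever the reason for not returning. The second is selection: if returning depends partly on how the eye responded to a lens, the analysis is restricted by something that happened after treatment. Each subject wears both lenses, so both eyes leave together and the comparison stays balanced. The subjects who remain may nevertheless be those who tolerated the lenses.

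The expectation of no drop-outs does not settle this. The length of one visit is a reason to expect subjects to finish that visit, not to attend four visits spread over about 4 months.

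**Working it through.** The plan has no figure to reproduce: it gives 50 subjects without an effect size, standard deviation, power or drop-out rate.

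**Inputs from the document.** 50 subjects (Exec Summary, Methodology). Phase 3 comes 2 months after the first fitting and Phase 4 comes 2 months after Phase 3, so completion takes 2 + 2 = about 4 months. **Assumed.** A probability q of not returning after each of Phases 1, 2 and 3, set at 2%, 5% and 10%.

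**Precision.**
- Measured in Phase 1: 50. Measured in Phase 2: 50(1 − q).
- Completers of all four phases: 50(1 − q)³.
- Growth in the Phase 1 standard error from using completers only: 1/√((1 − q)³).
- Growth for Phase 2, relative to those measured there: 1/√((1 − q)²) = 1/(1 − q).

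| q | Measured in Phase 2 | Completers | Phase 1 data sets discarded | Phase 1 SE ratio | Phase 2 SE ratio |
|---|---|---|---|---|---|
| 0 | 50 | 50 | 0 | 1.000 | 1.000 |
| 2% | 49.0 | 47.1 | 2.9 | 1.031 | 1.020 |
| 5% | 47.5 | 42.9 | 7.1 | 1.080 | 1.053 |
| 10% | 45.0 | 36.5 | 13.5 | 1.171 | 1.111 |

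In terms of power, take as an illustration the paired effect that gives 80% power with 50 subjects: (1.960 + 0.842)/√50 = 0.396 SD. By the normal approximation Φ(0.396√n − 1.960), Phase 1 power with completers only is 77.6%, 73.7% and 66.7% at the three rates.

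**Selection, if non-return follows a lens reaction.** Every input here is assumed. Let a fraction p of subjects react in Phase 1, let their Phase 1 reading differ from the others' by d SD (0.5 or 1), and let all of them leave. Set the mean over all fitted subjects to zero, with non-reactors at +pd and reactors at −(1 − p)d. The completers' mean is then pd. With the same people reacting each time, n = 50(1 − p) and the noncentrality of a t-test is pd√n. For d = 1:
- p = 1%: 0.01 × √49.5 = 0.070, two-sided rejection 5.05%
- p = 2%: 0.02 × √49 = 0.140, rejection 5.2%
- p = 5%: 0.05 × √47.5 = 0.345, rejection 6.3%
- p = 10%: 0.10 × √45 = 0.671, rejection 10.1%

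With d = 0.5 the last two are 5.3% and 6.2%. If reactions occur independently at each fitting, n is smaller and the rates are slightly lower (down to 6.0% at p = 10%, d = 0.5). Reversing the sign of d reverses the direction.

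These values depend on every reactor leaving. If only half leave (d = 1, same people reacting), the completers' mean at p = 10% is (45 × 0.1 − 2.5 × 0.9)/47.5 = 0.047 SD and rejection falls to 6.1%. At p = 5% it falls to 5.3%.

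**The case against.** The strongest objection is that completion may be meant phase by phase. Phase 1 ends with discharge from the study, Phase 2 likewise ("subjects will be discharged from the study before being called again in Phase 3"), and each phase describes its own analysis, as in "From the data collected, an analysis will assist to understand the mechanism of tear volume changes". On that reading no Phase 1 or Phase 2 reading is lost. This stands as a possible reading. The plan does not choose it, however, and two analysts could follow the same sentence to different sets. If that is the intention, the proposed wording simply states it.

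A second objection is that the sponsor expects nobody to leave. If so, the change costs nothing and alters nothing; if anyone does leave, the plan has no rule.

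A third objection is aimed at the selection argument, and it largely stands. The visible text recalls every subject, so no one is held back under the plan as written. No reaction or withdrawal rate is given. The zero-mean construction also gives non-reactors a real benefit of pd, so part of the excess rejection is a question of which population is of interest.

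A reader might also infer a safety defect, because Phases 1 to 3 set no tolerance condition before refitting and the later lenses are allocated at random. The documents do not support that as a demonstrated fault. Withdrawal wording may sit in pages removed before review, wear lasts 15 minutes, and a medical officer is on standby.

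**Conclusion.** The point holds as a small, worthwhile correction to the analysis set. On the natural reading, finished Phase 1 and Phase 2 data are discarded because of absence from later variability visits. The cost in Phase 1 precision is about 3%, 8% or 17% in the standard error at an assumed 2%, 5% or 10% non-return after each of Phases 1 to 3, and nothing if all subjects return. This holds whatever the reason for not returning, and it rests on completion meaning all four phases.

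A reader might go further and conclude that the rule biases the trial towards VCO or doubles its false-positive rate. The documents do not support that. The 10.1% figure needs a 10% reaction rate, a 1 SD gap and every reactor leaving, all together. At reaction rates of 1-2% the two-sided error stays at 5.0-5.2%. The bias could run either way, and nothing in the documents fixes its size.

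**What to change.** Under STATISTICAL ANALYSIS, replace the condition of having completed the study with *were fitted and measured in that phase*, applied to each endpoint: Phase 1 for TBUT and Phase 2 for Schirmer. The planned ANOVA uses three readings from one visit, so it needs no later attendance. For the variability objective, use only subjects with the repeat visits that the comparison requires. Report by phase how many subjects did not return and how many had a lens removed early, with reasons.

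This is a short amendment. Its downside is slightly different numbers of subjects across endpoints: at an assumed 5% non-return after each phase, 50 for Phase 1, 47.5 for Phase 2, 45.1 for Phase 3 and 42.9 for Phase 4. It does not remove all selection. A subject whose lens comes out early has no reading after 15 minutes' wear and would still be missing, which is why early removal should be counted. Nor does it recover readings from visits that were not attended.

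The sponsor may also wish to add a sentence requiring medical clearance before refitting an eye with a persistent reaction. That is an optional safety clarification, separate from the analysis-set change.

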## Methodology

The study will be conducted at Optometry clinic UKM KL. Random sampling and double mask method will be used as in this study. A total of 50 subjects who meet the inclusion criteria will be invited to participate in this study once the ethics has been granted. The purpose of the study will be explained to the subjects and consent will be taken if agreeable to participate in the study. Enrollment of subjects and clinical trial will be carried out in staggered period within 5 weeks for each phase.

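### The only named efficacy test applies only if a Shapiro-Wilk check passes; the check appears aimed at the values rather than residuals or paired differences, and no alternative is named if it fails

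*Combined protocol and SAP*

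**What the plan says.** The Statistical Analysis section sets the check: "Shapiro-Wilk test will be used to test the normality of the data as the sample size is less than 100". Repeated-measures ANOVA "will be used to analyze the statistical difference of before, immediately and after treatment if the data is normally distributed". The significance threshold is p < 0.05. The section gives no level for the normality test, no transformation, no alternative test, and no rule for the case where some sets of values pass and others fail. Nor does it say whether normality is judged on values, changes, between-eye differences or model residuals.

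The phase descriptions indicate what the data are. For Phase 1: "All tear breakup time (TBUT) measurements will be taken three times and the average value will be used as the data". Phases 2 to 4 use the same convention. In every phase each subject wears the VCO lens in one eye and the placebo lens in the other. Measurements are taken before insertion, on removal at 15 minutes, and again 15 minutes later.

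**The concern.** There are two linked problems.

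The first is the target of the check. On the natural reading, Shapiro-Wilk is applied to the averaged value for each eye and time. A repeated-measures ANOVA does not need those values to be normal. Its assumption concerns the within-subject residuals, or equivalently the differences between repeated measurements on the same person. Subjects may differ from one another in a skewed way while their differences behave well, and the stated rule would then set aside an analysis whose assumption is met.

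The second is what follows a failure. No other efficacy test is named, so the replacement would be picked with the data in view. The p < 0.05 threshold then no longer carries its nominal 5% error rate. Naming a fallback would cure this second problem but not the first.

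**Working it through.** **Inputs.** From the Methodology: "A total of 50 subjects who meet the inclusion criteria will be invited to participate in this study". Efficacy is assessed in completers, and the Phase 4 section expects that "the subjects will not have any 'drop-out' issues", so n = 50 is used. Two eyes at three times give 2 × 3 = 6 cells per phase. The documents give no mean, SD, distribution, effect size or power for TBUT or Schirmer, so there is no planned figure to reproduce. The 0.05 level for Shapiro-Wilk, and every distribution, coefficient of variation (CV) and correlation below, are assumptions.

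**Step 1: values against differences.** Write the value for subject i, eye e, time t as Y(i,e,t) = μ(e,t) + S(i) + ε(i,e,t). The paired quantity is

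D(i) = [Y(i,VCO,post) − Y(i,VCO,pre)] − [Y(i,control,post) − Y(i,control,pre)].

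S(i) cancels in D(i) and in each within-eye change, but stays in every Y. Skewness in S can therefore fail the check on Y without bearing on the test. Simulation: n = 50, 1,500 runs, S lognormal with mean 1 and the CV shown, ε normal with SD equal to half that CV. Share of runs failing Shapiro-Wilk:

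| CV of S | One cell | Any of 6 cells | Within-eye change | D |
|---|---|---|---|---|
| 0.2 | 19% | 49% | 5% | 4% |
| 0.3 | 34% | 71% | 6% | 5% |
| 0.5 | 61% | 88% | 6% | 4% |
| 0.8 | 79% | 97% | 6% | 6% |

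The differences fail at about the nominal rate while the values often fail.

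**Step 2: failure when everything is normal.** If k independent cells must all pass at 0.05, the chance of at least one failure is 1 − 0.95^k:

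- k = 1: 5%
- k = 3 (one eye, one phase): 1 − 0.857 = 14.3%
- k = 6 (one phase): 1 − 0.735 = 26.5%

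A simulation with correlated normal cells gave 25% for k = 6.

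**Step 3: failure when the error is skewed too.** With fully lognormal values (subject, eye and residual shares of log variance 0.60, 0.15 and 0.25), CV 0.2 to 0.8, one cell fails in 32% to 99% of runs and any of six in 78% to 100%. D fails in 9% to 73%. Differences fail less often than values at every CV, but checking them does not guarantee a pass.

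**Step 4: error cost of an open choice.** No true effect, lognormal values, log-scale within-subject correlation 0.6, n = 50, 6,000 runs (Monte Carlo margin about 1.96 × √(0.05 × 0.95 / 6,000) = 0.55 percentage points). Type I error:

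| Procedure | CV 0.3 | CV 0.5 | CV 0.8 |
|---|---|---|---|
| Paired t on D, no gate | 5.2% | 4.3% | 4.4% |
| Gate, Wilcoxon fixed in advance | 5.2% | 4.5% | 4.8% |
| Smaller p of t and Wilcoxon | 6.5% | 5.8% | 6.3% |
| Three-time ANOVA, no gate | 5.2% | 4.7% | 4.3% |
| Gate, Friedman fixed in advance | 5.5% | 4.7% | 4.8% |
| Smaller p of ANOVA and Friedman | 8.1% | 7.5% | 7.4% |

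The smaller-p rows treat the choice as always open between two candidate tests. Under the plan it opens only when the check fails.

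**The case against.** The strongest reply is that this is an ordinary omission. The section does not say at which level normality is tested, so a sensible analyst could check residuals, and a one-line fallback would bring the error rate back to about 5%. The second half stands: with the fallback fixed in advance, the gated procedure held 4.5% to 5.5%. The first half stands only in part. The section is silent on the level, but the phase descriptions attach the term to the averaged measurement and nothing points to residuals or differences. A fallback alone would still let the gate discard a valid ANOVA, as Step 1 shows.

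Four stronger readings are tempting, and the documents do not support them.

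- *The check will usually fail.* This needs a known degree of skew or a rule that many cells must all pass. The documents give neither. That the outcomes cannot be negative does not fix their skewness.
- *There is a 71% chance of failure across the study.* This is 1 − 0.95^24 for 24 cells. It assumes independence in repeated measurements on the same people, and a pass required in every cell of every phase. Phases 3 and 4 are variability repeats under objective (iii). Phases 1 and 2 alone give 12 cells and 1 − 0.95^12 = 46%, still under an unstated all-must-pass rule.
- *The p-value becomes uninterpretable.* The inflation found is to about 6% to 8% per comparison.
- *The analysis must be on the log scale.* The power ranking depends on the distribution assumed. For a 25% effect, log beats raw with lognormal data (74% against 70% at CV 0.5; 49% against 43% at CV 0.7), while raw beats log with gamma data (93% against 90%; 67% against 58%).

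**Conclusion.** The point holds in a limited form and should be corrected. The plan's only efficacy test depends on a normality check which, on the natural reading, looks at the averaged eye-by-time values instead of the residuals or within-subject differences that matter. No alternative is named if it fails. The rule can block a valid analysis: with skewed subject effects and normal within-subject error, at least one of six cells failed in 49% to 97% of runs, against 4% to 6% for the between-eye difference in change. It also leaves the replacement test open, at a cost of about 6% to 8% type I error per comparison if the smaller p is taken.

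These sizes rest on assumed distributions, and the actual failure rate cannot be derived from the documents. The figure of about 26% per phase under normality needs no skewness, but it does need six independent cells, a 0.05 level and an all-must-pass rule. The gate is not needed to protect the error rate: ungated tests at n = 50 on skewed data held 4.3% to 5.2%.

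**What to change.** - Delete the Shapiro-Wilk condition.
- For each outcome (TBUT and Schirmer), pre-specify one analysis: the per-subject VCO-eye minus control-eye change from pre-insertion, at one named post-wear time (on removal, or 15 minutes later). Test it with a paired t-test or the equivalent lens-by-time repeated-measures model, and report a 95% confidence interval.
- Report the Wilcoxon signed-rank test on the same differences as a fixed sensitivity analysis, whatever the distribution looks like.
- Use residual plots for description only, not to select a test.
- Fix the scale, raw or log, before the data are seen. If log is chosen, also fix any constant added for zero Schirmer readings, and note that with a constant the back-transformed effect is no longer a simple ratio. The log scale is optional.

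The cost is slightly more analysis text, no new data and no change to visits. The statistical downside is a small possible loss of power against a rank test if the differences are heavy-tailed; the fixed Wilcoxon analysis would show this.

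### The planned output for a paired-eye, placebo-controlled trial includes no VCO-minus-placebo difference with its uncertainty

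*Combined protocol and SAP*

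**What the plan says.** The STATISTICAL ANALYSIS section is the whole statistical plan. On presentation it says "All results are expressed as Mean" ± SD, with no condition attached. On testing, a repeated-measures ANOVA "will be used to analyze the statistical difference of before, immediately and after treatment if the data is normally distributed". A p-value below 0.05 "will indicate that the data is statistically significance". The efficacy set is completers: "The assessment of the efficacy will be based on the all subjects who completed the study".

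The design is given under Phases 1 to 4. Each subject is "fitted with therapeutic VCO contact lens on one of their eyes and a placebo hydrogel contact lens on the other eye", and the placebo eye is the control. Both eyes are measured before insertion, on removal after 15 minutes of wear, and again 15 minutes later. TBUT is measured in Phases 1, 3 and 4, and Schirmer in Phase 2.

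No section mentions a VCO-minus-placebo difference, an effect estimate, a standard error or a confidence interval. No numerical SD and no between-eye correlation is given.

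**The concern.** The trial is built around a comparison between the two eyes of one person, but the specified output contains no between-eye quantity. Two things are missing together. The ANOVA is described across time points with no lens factor, so its p-value may not address VCO against placebo at all. The summary format, if it is applied by eye and time, describes spread between people and says nothing about how precisely the between-eye difference is estimated.

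The Hypothesis section claims that the lens improves tear volume and stability. Judging that claim needs the size of the benefit over placebo and its uncertainty. Without an interval, a non-significant result cannot be told from an imprecise one, and no justification is given for 50 subjects that would help. The format is also unconditional, although the same section allows that the data may not be normal. No summary is named for skewed data.

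**Working it through.** The plan gives no precision or sample-size figure, so there is none to reproduce. The check asks whether the interval can be recovered from per-eye means and SDs, and how wide it would be.

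**Inputs**
- n = 50 subjects, so 50 eye pairs (Methodology). No allowance for loss is made: Phase 4 says "the subjects will not have any 'drop-out' issues". Results for 40 and 30 completers are shown for sensitivity.
- A common per-eye SD, used as the unit because the documents state none. If change from baseline is analysed, it is the per-eye SD of the change.
- Between-eye correlation r of the quantity analysed. It is not in the documents, so it is **assumed** and varied.

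**Formulas**
- SE of the mean paired difference = SD × √(2(1 − r)/n)
- 95% half-width = t(0.975, n − 1) × SE, with t = 2.010 for n = 50

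**Half-width at n = 50, in per-eye SD**

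| r (assumed) | SE | Half-width |
|---|---|---|
| 0 | √(2/50) = 0.200 | 0.402 |
| 0.3 | √(1.4/50) = 0.167 | 0.336 |
| 0.5 | √(1/50) = 0.141 | 0.284 |
| 0.7 | √(0.6/50) = 0.110 | 0.220 |
| 0.8 | √(0.4/50) = 0.089 | 0.180 |
| 0.9 | √(0.2/50) = 0.063 | 0.127 |

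For r from 0.3 to 0.7, the half-width is 0.378 to 0.248 SD with 40 completers and 0.442 to 0.289 SD with 30.

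**Can the interval be recovered?** Hold the printed table fixed: the same mean and SD in each eye, with an observed difference of 0.3 SD and n = 50. Only r changes.

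| r (assumed) | t = 0.3/SE | p | 95% CI (SD) |
|---|---|---|---|
| 0 | 1.50 | 0.14 | −0.10 to 0.70 |
| 0.5 | 2.12 | 0.039 | 0.02 to 0.58 |
| 0.8 | 3.35 | 0.0015 | 0.12 to 0.48 |

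The point difference is the same in each row because it follows from the means. The interval and the conclusion are not, because r does not appear in the table.

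**Number of contrasts.** TBUT in three phases at two post-wear times gives 6. Schirmer in one phase at two times gives 2. The total is 8.

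**The case against.** The mean ± SD line is an ordinary statement of descriptive format. It excludes nothing, so the gap is an omission and not a rule against effect estimates. This stands.

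A crude effect size is available. Each completer contributes both eyes, so the difference of the two eye means equals the mean paired difference. This stands too; what is missing is its uncertainty.

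Recovery fails only on one reading of the format. If the SD of the paired difference were shown, the half-width would be 2.010/√50 = 0.284 of that SD. An exact p-value for the lens contrast would also return the SE. Both are correct, but the plan specifies neither: it names no paired difference, and its ANOVA is described over time only.

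A reader might infer that a ± SD range is several times too wide. At n = 50 the per-eye SD is indeed about 3.0 to 4.5 times the half-width for r from 0.3 to 0.7. But the plan never offers the SD as a measure of precision, and an SD describes spread between people, which is a different quantity. The ratio shows no bias, lost power or wrong conclusion in the plan, and it is not part of this point.

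**Conclusion.** The point holds as a gap in the specified output. Followed exactly, the plan yields per-time summaries and a time-based p-value. It yields no estimate of the VCO-minus-placebo difference with its uncertainty, although the fellow eye is fitted with "a placebo hydrogel contact lens on the other eye which acts as a control". That the interval cannot be recovered assumes that results are shown by eye and time, and does not depend on any particular correlation.

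The size of what is missing does depend on assumption: a 95% half-width of about 0.34 to 0.22 per-eye SD for r from 0.3 to 0.7 with all 50 subjects, and wider if fewer complete.

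The documents do not support the stronger readings that the plan bars effect estimates, that no effect size at all could be obtained, or that the SD is wrong as a description. The change is worth making because the trial's own question cannot be properly answered from the planned output; data collection is unaffected.

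**What to change.** Add to the STATISTICAL ANALYSIS section:
- For TBUT (Phase 1, with Phases 3 and 4 as repeats) and Schirmer (Phase 2), at each post-wear time, report the mean within-subject VCO-minus-placebo difference in change from the pre-insertion value, with its 95% confidence interval and p-value.
- State that this paired contrast, and not the ANOVA over time, is the basis for the VCO conclusion.
- Name in advance which contrast or contrasts decide, because up to eight would be reported and no multiplicity rule exists.
- Keep mean ± SD by eye and time as description, with median and quartiles where the distribution is skewed.

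The cost is a small amount of extra analysis and a decision on the deciding contrast before the data are seen. No new measurements or subjects are needed, since the baseline and both eyes are already recorded. It is more than a presentation edit, because it settles which analysis answers the VCO question.
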